1.0 Objectives

1.1 Study Objectives

The objective of this study is to test the effect of a range of doses of a novel nicotine film on plasma nicotine levels and, via a questionnaire, subjective ratings of the film and side effects. We predict that delivery of nicotine via the film will produce plasma nicotine levels akin to other methods of nicotine replacement therapy (NRT) and that it will be easy to use, safe, and well tolerated. The nicotine film is not part of standard of care and is not available in a non-investigational setting in the United States.

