1.2 Primary Study Endpoints

The primary endpoint is plasma nicotine.

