7.0 Study Design and Procedures

7.1 Study Design

This will be a randomized, double blind, parallel group pharmacokinetics study that will occur in two parts. The researchers and participants will be blind to the dosing of the nicotine films. Participants may participate in one or both parts of the study.

Part I: Participants are randomized to receive one dose of 0, 2, or 4 mg nicotine films

Part II: Participants are randomized to receive one dose every three hours for a total of four doses of either all 0 mg, all 2 mg or 4,4,0,4 mg nicotine films.

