9.0 Statistical Plan

9.1 Sample size determination

Initial testing by [name] (a principal investigator on the project and co-inventor of the oral nicotine film) has demonstrated that the plasma nicotine levels produced by oral nicotine film are comparable in size to those produced by consumption of a similar dose of Nicorette gum. Pharmacokinetic studies have shown that Nicorette gum has robust effects on plasma nicotine concentration that are readily detectable in sample sizes that are approximately the same as (e.g., Benowitz, Jacob, & Savanapridi, 1987; Lunell & Lunell, 2005), or smaller than (e.g., Shiffman et al., 2009), the one proposed here (n=12). Based upon such work, we are confident that we will have sufficient power to achieve the aim of the proposed research.

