9.2 Statistical methods

Paired sample t-test (or nonparametric Wilcoxon Rank-Sum test) will be used to examine the changes in the outcome measures (plasma nicotine, subjective measures, HR, BP) from the baseline.

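### The planned change-from-baseline test does not address the prediction that film nicotine levels will resemble other NRT, and the power assurance counts 12 people when only four receive each dose

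*Combined protocol and SAP*

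**What the plan says.** Section 1.1 gives the objective as to "test the effect of a range of doses of a novel nicotine film on plasma nicotine levels". The next sentence predicts levels "akin to other methods of nicotine replacement therapy (NRT". Section 1.2 says only that "The primary endpoint is plasma nicotine", with no summary parameter, time point or threshold.

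The arms are all film regimens. In Part I of section 7.1, "Participants are randomized to receive one dose of 0, 2, or 4 mg nicotine films"; in Part II the four-dose sequences are "either all 0 mg, all 2 mg or 4,4,0,4 mg nicotine films". Sections 7.2 and 7.4.2 put four participants in each Part 2 group, and 7.2 does the same for Part 1. Section 3.2 excludes anyone who used NRT in the past week.

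Section 9.2 plans a paired t-test or a Wilcoxon test, which "will be used to examine the changes in the outcome measures (plasma nicotine, subjective measures, HR, BP) from the baseline". Section 11.7 repeats this for safety and adds no other comparison.

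Section 9.1 says that the film is comparable with a similar dose of gum, that the effect of gum on plasma nicotine is readily detected in samples about the size proposed (n=12) or smaller, and that "we are confident that we will have sufficient power to achieve the aim of the proposed research". It gives no significance level, effect size, SD or margin.

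**The concern.** A prediction of similarity needs something to be similar to and a rule for how close is close enough. The plan supplies neither. Its one test asks whether a participant's nicotine differs from that participant's own baseline. A film delivering well under gum levels could pass it, and so could one delivering well over. A non-significant result would not show dissimilarity either.

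What is at stake is the wording of the conclusion. With a similarity prediction in the objectives, a baseline test in the analysis section and an assurance of power between them, a significant rise could be presented as support for the prediction. If a published NRT figure were brought in later, its product, parameter and value could be chosen after the film results were known.

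**Working it through.** **1. The plan's own figure.** The n=12 in 9.1 cannot be reproduced: there is no significance level, power, effect size, SD or margin to put into a formula. Everything below that needs a CV, a margin or a 5% level rests on an assumption.

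**2. Is an NRT benchmark given anywhere?**

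| Place | What it gives | Usable as an NRT reference? |
|---|---|---|
| 2.3 | 1 mg film raises plasma nicotine by less than 2 ng/ml | No: a film, and not a study dose |
| 2.3 | Up to 50 ng/ml on a typical smoking day | No: smoking |
| 2.3 and 9.1 | Film comparable with a similar dose of gum | Names a product, but no concentration, parameter or margin |
| 11.6 | Part 1 nicotine results reviewed before Part 2 | No benchmark stated |

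**3. What the paired test responds to.** The statistic is t = mean change / (SD of change / √n). Suppose the SD of change is 40% of the mean change. With n = 4, t = 1 / (0.40 / 2) = 5.0, against a two-sided 5% critical value of 3.182 on 3 df. The mean change cancels, so a small, moderate or large rise gives the same t. Noncentral-t power at n = 4 is 99%, 90% and 76% when the SD of change is 30%, 40% and 50% of the mean change, whatever the level reached. Significance therefore carries no information about position relative to NRT.

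**4. Twelve against four.** Twelve is the total in a part; four are on 0 mg and four on each active dose or regimen. Section 9.2 does not say whether the test is run by dose or pooled. For a single group:

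| n | 95% half-width, t(0.975, n−1)/√n, in SDs of change | Mean change for 80% power, in SDs of change |
|---|---|---|
| 4 | 1.59 | 2.13 |
| 12 | 0.64 | 0.89 |

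The interval at four is about 2.5 times as wide as at twelve (1.59 / 0.64). Pooling all twelve would not give the second row for an active dose, because a third of those people receive no nicotine from the film.

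**5. Precision of a dose estimate at n = 4.** On the log scale, SD = √ln(1 + CV²) and half-width = 3.182 × SD / √4.

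- CV 30%: SD = √ln 1.09 = 0.294; half-width 0.467; limits 0.63 to 1.60 times the geometric mean, about 2.5-fold from end to end.
- CV 50%: SD = √ln 1.25 = 0.472; half-width 0.752; limits 0.47 to 2.12 times, about 4.5-fold.
- Over CV 20% to 60%, the end-to-end width runs from 1.9-fold to 5.8-fold.

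**6. How much depends on the definition of similarity.** For a concurrent NRT arm, with two one-sided 5% tests, a true ratio of 1, 80% power and an assumed CV of 30%, the normal approximation gives n per arm = 2 × SD² × (1.645 + 1.282)² / (ln margin)². This is 30 for limits of 0.80–1.25, 9 for 0.67–1.50 and 4 for 0.50–2.00; the smallest figure is optimistic because the approximation is poor there. Whether four per group could address similarity thus depends on a definition that the plan does not give.

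**The case against.** The strongest reply is that similarity to NRT is not the objective. Section 1.1 sets out to examine the effect of film doses, and the sentence about NRT is an accompanying prediction. Change from baseline bears on that objective, at least in part. This stands, and it limits the point to how the prediction may be interpreted. A reader might infer that the whole objective goes untested; the documents do not support that.

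A reader might also infer that the prediction can never be confirmed or refuted. That goes too far. Gum at a similar dose is named as a qualitative reference, plasma is sampled densely, and levels could be set informally beside published ones; very low levels would count against the prediction. What holds is that the planned analysis does not do this.

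Two more inferences should be resisted. No section says that a rise will be reported as similarity; it could be. And a strict range such as 0.80–1.25 is not proposed anywhere, so failing it would not show that the prediction is wrong.

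Finally, 9.1 argues about detecting a rise, and its reference to the aim need not mean similarity. That is fair. It also means that 9.1 offers no support for the similarity prediction. The mismatch between twelve and four is a separate weakness of the power assurance.

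**Conclusion.** The point holds for the planned analysis. Carried out as written, 9.2 cannot support the prediction about NRT in 1.1, because the plan has no NRT arm, reference value or criterion and the test statistic does not depend on the level reached. This follows from the text and needs no assumption.

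The power assurance in 9.1 is unquantified and counts twelve where four receive each dose. The size of that problem, a 95% CI about 2.5-fold to 4.5-fold wide for a dose's geometric mean, rests on assumed CVs of 30% to 50% and on a log-scale summary such as Cmax or AUC, neither of which the documents specify. A paired test at four per dose could still detect a rise that is large relative to its SD, so the study is not shown to be unable to detect nicotine delivery.

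The consequence concerns what may be concluded; conduct and data collection are unaffected.

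**What to change.** - **Sections 1.1 and 9.2:** state the aim as estimating plasma nicotine by film dose. Name the parameters (for example baseline-corrected Cmax and AUC), report the geometric mean with 95% CI for each dose, and add a comparison against the 0 mg group, which is randomised but has no between-group comparison in 9.2. State that no conclusion of similarity to NRT will be drawn from the change-from-baseline test.
- **If the NRT comparison is kept:** before data are seen, fix the product, dose, PK parameter and a sourced published value, and show it beside the Part 1 single-dose estimates as descriptive only. A single-dose value does not match the repeated dosing of Part 2. The gum studies cited in 9.1 are not in the section 23 reference list, and whether they report a suitable value cannot be seen from the documents; the source should be added with the value.
- **Section 9.1:** replace the power assurance with the expected precision at four per dose, with the assumed CV stated and justified.

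The cost is a small amount of added analysis and a less favourable stated claim. No new arm, participants or blood samples are needed.

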1.2 Primary Study Endpoints

The primary endpoint is plasma nicotine.

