7.2 Study Procedures

Part 1- Screening (Phone)

Participants will be instructed to drink water prior to their visit to help the blood draw process go smoothly. They will also be instructed that they may choose to have a meal from our cafeteria but may also bring snacks if they would like. Participants will also be informed that they can bring personal items such as laptops, books, etc. for use during their visit.

Part 1-Screening (In Person)

Participants will be re-screened for eligibility and informed consent for the appropriate part of the study will be obtained by research staff.

After consent, additional eligibility screening materials will include:

1. A review of medications and medical history
2. NIDA Drug Screener
3. Blood Pressure (systolic must be \leq 140, diastolic must be \leq 90)
4. Urine pregnancy test (if applicable)
5. Exhaled Carbon Monoxide <12 ppm

Part 1 Visit – 4 Hours

Clinical measures and questionnaires will be conducted as outlined in the table below. An IV will be inserted for access for 11 blood draws in Part 1.

Part 1: Time and Events Table						
	Screening	Part 1 Procedures				
Visit Hour	-2	-1	0	1	2	3
Administer Film			X			
Blood Draws (mins)			0-59	60-119	120-179	180-239
Baseline Blood		X				
Hour 0 Blood			Set Minutes: 5, 10, 20, 30, 40, 50 Varied by Participant: 1 minute after film dissolves			
Hour 1 Blood				Minute 60		
Hour 2 Blood					Minute 120	
Hour 3 Blood						Minute 180
Measures						
Screener 2	X					
Concomitant Meds	X					
Medical History	X					
NIDA	X					
CES-D		X				
Oropharyngeal Exam		X				X
Blood Pressure & Heart Rate	X	X	Minute 30	Minute 0, 30	Minute 0, 30	Minute 0, 30
CO Reading	X					X
Pregnancy Test	X					
Anthropometrics		X				
Demographics		X				
Nicotine Dependence		X				
Cigarette Details		X				
Tobacco Use History		X				
Minnesota Withdrawal Scale		X	Minute 15, 35, 55	Minute 20	Minute 20	Minute 20
Questionnaire of Smoking Urges		X	Minute 15, 35, 55	Minute 20	Minute 20	Minute 20
Study Product Side Effects			Minute 15, 35, 55	Minute 20	Minute 20	Minute 20
Study Product Evaluation						X
Likelihood of Use Scale						X
Payment						\$120

Film Administration, Dose and Blood Draws:

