Participants will receive one film at this visit after completing baseline measures (approximately 8 AM). They will be instructed to allow the film to dissolve in their mouth without chewing or swallowing it and to report to the researcher when he or she feels that the film has completely dissolved. Four participants each will receive a randomly allocated dose of either (a) 0mg, (b) 2mg or (c) 4mg oral nicotine film. The Time and Events table above details the order of events and timing for biomeasures, questionnaires and 11 total blood draws. However, if the film dissolves within one minute of a set blood draw time, the blood draw that is to be completed one minute after the film dissolves will be omitted.

Payment:

Participants will receive \$120 for completing this visit.

Part 2- Screening (Phone)

Participants will be instructed to drink water prior to their visit to help the blood draw process go smoothly. They will also be instructed that they may choose to have meals from our cafeteria but may also bring snacks if they would like. Participants will also be informed that they can bring personal items such as laptops, books, etc. for use during their visit.

Part 2- Screening (In Person)

Participants will be re-screened for eligibility and informed consent for the appropriate part of the study will be obtained by research staff.

After consent, additional eligibility screening materials will include:

1. A review of medications and medical history
2. NIDA Drug Screener
3. Blood Pressure (systolic must be \leq 140 mm Hg, diastolic must be \leq 90 mm Hg)
4. Urine pregnancy test (if applicable)
5. Exhaled Carbon Monoxide <12 ppm

Part 2 Visit- 12 hours

Clinical measures and questionnaires will be conducted as outlined in the table below.

An IV will be inserted for access for 20 blood draws in Part 2. Time and contents of participant meals/snacks will also be recorded so as to enable researchers to assess food intake and timing as it relates to timing of nicotine absorption from the film.

Part 2: Time and Events Table														
	Screening		Part 2 Procedures											
Study Hour	-2	-1	0	1	2	3	4	5	6	7	8	9	10	11
Administer Film			X			X			X			X		
Blood Draws														
Baseline Blood		X												
Hour 0 Blood			Min 30, 45											
Hour 1 Blood				Min 0										
Hour 2 Blood					Min 0									
Hour 3 Blood						Set Mins: 0, 30, 45								
Hour 4 Blood							Min 0							
Hour 5 Blood								Min 0						

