Hour 6 Blood									Set Mins: 0,30,45					
Hour 7 Blood										Min 0				
Hour 8 Blood											Min 0			
Hour 9 Blood												Set Mins: 0, 30,45		
Hour 10 Blood													Min 0	
Hour 11 Blood														Min 0
Study Hour	-2	-1	0	1	2	3	4	5	6	7	8	9	10	11
Measures														
Screener 2	X													
Concomitant Medications	X													
Medical History	X													
NIDA	X													
CES-D	X													
Oropharyngeal Exam		X												X
Blood Pressure & Heart Rate	X	X	Min 30	Min 0, 30	Min 0, 30	Min 0, 30	Min 0, 30	Min 0, 30	Min 0, 30	Min 0, 30	Min 0, 30	Min 0, 30	Min 0, 30	Min 0
CO Reading	X													
Pregnancy Test	X													
Anthropometrics	X													
Demographics	X													
Dependence	X													
Cigarette Details	X													
Tobacco Use History		X												
Minnesota Withdrawal Scale		X	Min 50	Min 50		Min 50	Min 50		Min 50	Min 50		Min 50		Min 50

Questionnaire of Smoking Urges		X	Min 50	Min 50		Min 50	Min 50		Min 50	Min 50		Min 50	Min 50
Study Product Side Effects			Min 50	Min 50		Min 50	Min 50		Min 50	Min 50		Min 50	Min 50
Study Product Evaluation						Min 0							X
Likelihood of Use Scale						Min 0							X
Dose Awareness													X
Payment													\$240

Film Administration, Dosing and Blood draws:

Participants will receive four doses of nicotine film during this visit. Four participants each will be randomly allocated to consume four films over twelve hours in the following orders (a) 0,0,0,0mg (b) 2,2,2,2, or (c) 4,4,0,4. The first film will be administered upon completion of baseline measures (approximately 8AM). Again, participants will be instructed to allow the film to dissolve in their mouth, without chewing or swallowing it and to report to the researcher when he or she feels that the film has completely dissolved. Films will be administered every three hours (approximately 11 AM, 2 PM, and 5 PM). The Time and Events table above details the order of events and timing for biomeasures, questionnaires and 20 total blood draws.

Payment:

Participants will receive \$240 for completing this visit.

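### The primary endpoint names no summary, time point or contrast, and the one planned test (change from baseline) does not use the randomised 0 mg arm

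*Combined protocol and SAP*

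**What the plan says.** Section 1.2 defines the endpoint in one sentence: "The primary endpoint is plasma nicotine". It names no AUC, Cmax, Tmax, time point or contrast.

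Section 9.2 gives the whole analysis: "Paired sample t-test (or nonparametric Wilcoxon Rank-Sum test) will be used to examine the changes in the outcome measures", measured from baseline. Section 11.7 repeats it for safety data. Neither section says which draws enter the test, how repeated draws are combined, or whether arms are analysed separately or pooled. No significance level or multiplicity rule is given.

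Blood is sampled densely (section 7.2). For Part 1: "An IV will be inserted for access for 11 blood draws in Part 1". The hour 0 row of the Part 1 table reads "Set Minutes: 5, 10, 20, 30, 40, 50 Varied by Participant: 1 minute after film dissolves". If dissolution falls within a minute of a set draw, "the blood draw that is to be completed one minute after the film dissolves will be omitted". Part 2 has "20 total blood draws". Each part randomises four participants to each of three groups, one of them 0 mg. Section 1.1 sets the objective as the effect of a range of doses.

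**The concern.** A serial concentration profile is not an endpoint until someone says how it becomes one value per participant and what that value is compared with. Here both choices are open, so a draw, a summary or a test could be chosen once the concentrations are known.

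The contrast is the larger problem. A change from baseline within an arm does not estimate a dose effect. Participants smoke more than 9 cigarettes a day (section 3.1) and stay on site for about 4 or 12 hours (sections 7.3 and 7.4.4), so their plasma nicotine may fall whatever the film does. Section 2.3 reports a rise of under 2 ng/ml from a 1 mg film, against levels of up to 50 ng/ml in smokers on a typical day. A rise of 2 ng/ml is cancelled by a 4% fall from 50 ng/ml (2/50), or a 20% fall from an assumed 10 ng/ml (2/10). The 0 mg arm would show that drift, but the stated analysis does not use it. An inert film could then appear to lower nicotine, and real delivery could be masked.

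**Working it through.** **Plan's own figures.** The n=12 per part in section 9.1 cannot be reproduced, because no significance level, power, effect size or SD is given. The draw counts do reproduce from the tables in section 7.2:

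- Part 1: 1 baseline + 6 set + 1 at dissolution + 3 (minutes 60, 120, 180) = 11, so 10 post-baseline (9 if the dissolution draw is omitted).
- Part 2: 1 baseline + (2+1+1) + (3+1+1) + (3+1+1) + (3+1+1) = 20, so 19 post-baseline.

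**Check 1: every draw tested, flat true level.** Assumptions, none from the plan: each draw tested separately, paired t-test, two-sided 0.05, n=4 (3 df), no true change, normal data, one shared baseline, dissolution draw at minute 8. With independent tests the chance of at least one p<0.05 would be 1-0.95^10 = 40.1% and 1-0.95^19 = 62.3%. The shared baseline and serial correlation lower this. Simulation (60,000 runs) gives:

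| Correlation between draws | Part 1, any change | Part 1, increase | Part 2, any change | Part 2, increase |
|---|---|---|---|---|
| None beyond shared baseline | 33.8% | about 17% | 49.3% | 25.7% |
| Half-life 15 min | 32.2% | 16.8% | 48.3% | 25.1% |
| Half-life 60 min | 30.5% | 15.6% | 43.0% | 22.3% |
| Half-life 240 min | 29.5% | 15.2% | 36.7% | 19.0% |
| Baseline variance doubled | 28.6% | 14.3% | 40.2% | 20.7% |

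A separate set of runs gave 27-32% and 38-49% for any change, and 14-16% and 20-26% for an increase. Together the ranges are 27-34% and 37-49% (any change), and 14-17% and 19-26% (increase). One pre-specified test per arm would give 5%, or 2.5% for an increase.

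**Check 2: the test the plan leaves open.** A rank-sum test of 4 v 4 values at every draw gives 17.9% (Part 1) and 26.2% (Part 2) with independent values. A signed-rank test with n=4 has a minimum two-sided p of 2/2^4 = 0.125, so it can never reach 0.05.

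**Check 3: falling residual nicotine.** Assumptions: an inert film, washout half-life 1-3 h, baseline CV 0.3-1.0, 10% assay noise, n=4.

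- At least one significant draw appears in about 54-99% of arms, nearly all decreases. A significant increase appears in about 0-3%.
- Testing the last draw alone still gives a significant change in about 42-99% of arms. One pre-specified within-arm test therefore does not cure the problem.
- A within-arm test of AUC change was significant in about 65-80% of arms in runs over the same half-lives. This rate is lower when the baseline spread is wide and higher when it is narrow. Comparing the same AUC with a 0 mg arm gave about 4%.

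**The case against.** The strongest reply is that the plan never says every draw will be tested. That is correct. A reader might infer that the plan's rule carries a 30-49% false-positive rate. The documents state no such rule, so Check 1 shows what would follow under one reading.

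Three further points stand.

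- Only an increase suggests delivery, so the any-change rate is about twice the relevant one.
- Compounding it over all three arms would overstate the risk, because a change in the 0 mg arm is not evidence for the film. For increases in the two active arms alone, taken as independent, 1-0.85^2 to 1-0.83^2 gives 28-31% in Part 1, and 1-0.81^2 to 1-0.74^2 gives 34-45% in Part 2.
- A flat level is doubtful in daily smokers. Under washout false increases nearly vanish.

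A reader might also infer that the dense sampling would go unused, or that p-values decide the move to Part 2. The documents support neither: they are silent on summaries, and section 11.6 has the leadership group review all Part 1 data, including blood nicotine, before Part 2 begins.

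None of this supplies the missing definition or contrast. Washout weakens the multiplicity argument but strengthens the case against a within-arm test. The carbon monoxide limit of 12 ppm in section 3.1 restricts recent smoking, but the plan sets no ceiling on baseline plasma nicotine. The mention of a rank-sum test does not imply a comparison of arms either, since section 9.2 offers it as the alternative to the paired t-test of change from baseline.

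**Conclusion.** The point holds as an undefined primary endpoint with an analysis that cannot answer the study's question. This rests on the text alone: no summary, time point or contrast is named, and the one stated test ignores the randomised 0 mg group.

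The error rates are conditional. They assume two-sided 0.05, arms of 4 and paired t-tests, with either every draw tested against a flat level (27-34% and 37-49% for any change; 14-17% and 19-26% for an increase) or an assumed washout (54-99% for any change, nearly all decreases; 0-3% for an increase). They show how far the result depends on choices not yet made, and do not give the plan's actual false-positive rate. Confidence is high in the defect and moderate at best in any single figure. It should be settled before unblinded concentrations are examined.

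**What to change.** In sections 1.2 and 9.2:

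- **Summary.** Name one primary value per participant. Part 1: AUC 0-180 min. Part 2: AUC 0-11 h, supported by AUC over the 2 h after each film, a window sampled after all four films. Use actual draw times, take the baseline draw as the starting value, and say how an omitted dissolution draw is handled.
- **Baseline.** State whether it enters as a covariate or by subtraction.
- **Contrast.** Compare each active group with 0 mg in one model: 2 mg and 4 mg in Part 1; 2,2,2,2 and the 4,4,0,4 sequence in Part 2. Lead with estimates and 95% CIs.
- **Multiplicity.** State the significance level and fix the order of the two contrasts, for example higher-dose group first, testing the second only if the first succeeds. If an exact permutation test is the fallback, its minimum two-sided p for 4 v 4 is 2/70 = 0.029. That can meet 0.05 in an ordered sequence but never a Bonferroni level of 0.05/2 = 0.025.
- **Support.** Compare Cmax between arms only. The largest of 10 or 19 draws exceeds a single baseline draw through noise alone, so a test against baseline is biased upward. Report individual draws descriptively, without p-values.

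The cost is wording; no new data are needed. Time-point p-values stop being primary evidence. With 4 per arm the intervals will be wide, and the text should say so.
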